### **IRB** Protocol

### Multimodal Post-Cesarean Analgesia with Spinal Morphine and Continuous Wound Infiltration of Ropivacaine Using the OnQ® Elastomeric Pump: A Dose-Ranging Study Using a High-Volume, Low-Dose Protocol PI: [name]

Abstract:

The purpose of the proposed study is aimed to determine whether continuous subfascial infusion of ropivacaine using the On-O® elastomeric pump in combination with intrathecal (IT) preservative-free morphine (PFM) will improve post-operative cesarean section pain relative to IT PFM alone (the current standard of care). Using a doubleblinded, randomized, placebo-controlled study design, 60 women undergoing their first, second or third cesarean section will be randomly assigned to one of 3 different groups receiving either saline (control, n=20) or ropivacaine (0.1% or 0.2%, experimental groups n=20 in each) subfascially via the elastomeric pump. We will enroll up to 70 subjects to achieve 60 randomized and treated subjects, to account for screen failures and/or early terminations, All participants will receive an IT dose of 200mcg of PFM as part of a standardized spinal anesthetic for their operative procedure. During closure of their abdomen, all patients will undergo placement of a multi-orifice, silver-impregnated catheter in the subfascial space. At the conclusion of the surgery, the catheter will be bolused with 8ml of one of the three test solutions, after which an On-O® elastomeric pump (containing the same solution as initially administered through the catheter) will be attached to infuse the test solution at a rate of 8ml/hr. The infusion system will then be left in place for up to 72hr. Adjunctive pain medicines (ketorolac, morphine, ibuprofen, and oxycodone-acetaminophen) will be available for the treatment of breakthrough pain during hospitalization. The primary outcome being measured in the study is postoperative pain with movement as assessed immediately after the study bolus (baseline) and during the immediate post-operative period, when leaving the PACU (2hr), 6hr, 12hr, 24hr, 48hr, and 72hr post-op. Pain will also be evaluated by telephone at 4-6 weeks and 3mo after surgery. A visual acuity pain scale (VAPS) will be used to measure patient pain levels while hospitalized whereas pain at the 4-6 week visit and 3mo will be quantitated using a numeric pain scale (NPS). Secondary outcomes to be studied include degree of pain at rest, time to first rescue medication, time to first opioid use, amount of

inpatient non-steroidal anti-inflammatory drug (NSAID) use, amount of inpatient opioid use, incidence and severity of opioid systemic side effects, incidence and severity of local anesthetic side effects, catheter related issues, breast feeding success, maternal satisfaction, evaluation of wound healing, categorization and quantification of outpatient pain medication, and cost analysis.

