# **Participant Selection**

The study will take place at Emory University Hospital Midtown (EUHM), which cares for a mixed community- and university-based obstetric practice. Parturients will be recruited from the patient pools of both private and Emory physicians, and enrolled after appropriate consent has been obtained. The inclusion criteria for the study includes all ASA class I-III parturients at least 34 weeks pregnant, that are 18 years or older, have never had a cesarean section, have had one or two prior cesarean sections, and are undergoing scheduled or unscheduled non-emergent cesarean sections with spinal anesthesia. Exclusion criteria includes parturients who have allergies to morphine, ketorolac, or amide local anesthetics; pregnancies less than 34wks gestational age; significant maternal cardiac, liver, or renal disease; maternal history of narcotic abuse or dependency; presence of a pre-operative fever ( $\geq 100.4$  °F); emergent cesarean sections with or with-out general anesthesia; and patients in whom valid consent is questionable (non-English speakers or mentally-impaired individuals). Study patients have the option of withdrawing from the study at any point, as the On-Q® pump infusion can be simply discontinued and the catheter removed. At such time the patient would revert to our standard pain management protocol.

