# **Statistical Analysis**

Based on a preliminary sample size calculation using an  $\alpha$  risk of 0.05, a  $\beta$  risk of 0.2, and an effect size involving a 40% reduction in pain scores, we estimate that 20 patients are needed in each arm of the study. Data normality will be tested using the Kolmorgorov-Smirnov test. Normally distributed data will be presented as means  $\pm$  SD, whereas non-normally distributed data will be expressed as medians with interquartile ranges. Categorical data will be reported as frequencies. VAS scores will be analyzed using two-way ANOVA for repeated measures. Non-normal data will be analyzed using the Friedman test. Categorical data will be analyzed using the X test. Multiple comparisons will use a Bonferroni correction. Differences will be considered statistically significant at a P<0.05.

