Additionally, patients in the study will be immediately unblinded via phone call to the pharmacy in the three following situations: a) if they experience any 2 of 4 minor LA toxicities (perioral numbness, metallic taste in mouth, tinnitus, or light-headedness); b) any signs of severe systemic toxicity (seizures, arrhythmia, obtundation, cardiac arrest); or allergic reactions which appear by timing as due to LA administration (hives, angioedema, anaphylaxis). Minor toxicities will be treated by simply stopping the infusion and watching the patient for 6hr (approximately 3 half-times in circulation - product insert). Major toxicities will be treated by stopping the infusions and providing

appropriate supportive or resuscitative care. It is felt that major toxicity is very unlikely considering the drug utilized, the drug dosage, the use of a clinically-approved delivery device, and the restrictions on recruiting patients with LA allergies.

The OnQ® elastomeric pump and silver-impregnated catheter are FDA-approved devices for the treatment of post-surgical pain after all types of surgery including cesarean section. Theoretically, it could be argued that there is a small risk of skin or wound infection due to the presence of a tunneled percutaneous catheter for three days. This risk will be mitigated in three ways. First, sterile technique will be used throughout the procedure and the patients will be given antibiotic prophylaxis before the cesarean section. Second, the silver-impregnated catheter has inherent antimicrobial properties which prevent formation of a bacterial microfilm with subsequent catheter colonization; and also elutes silver directly into the implantation site where it may have direct antimicrobial activity (31). Finally, LAs themselves have intrinsic bacteriostatic and/or bactericidal properties against a wide range of pathogenic bacteria, and thereby continuous wound infusion with these agents might create an unfavorable milieu for infection (32).

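### The over-enrolment wording leaves room to replace or drop women who stop after the study bolus, which could select the comparison on a post-randomization outcome

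*Combined protocol and SAP*

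**What the plan says.** The abstract plans that "60 women undergoing their first, second or third cesarean section will be randomly assigned to one of 3 different groups", with 20 per arm. The next sentence sets the enrolment cap: "We will enroll up to 70 subjects to achieve 60 randomized and treated subjects, to account for screen failures and/or early terminations". It gives no split of the extra ten between the two reasons.

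Under Study Design and Methodology, the arm is assigned before the spinal anesthetic is started. The bolus is given at the end of surgery and the pump is then attached. The abstract allows the infusion system to stay in place for up to 72 hours.

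Three later sections bear on women who stop:

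- Participant Selection: "Study patients have the option of withdrawing from the study at any point", the explanation being that the pump is easily stopped and the catheter taken out. It continues: "At such time the patient would revert to our standard pain management protocol".
- Patient Safety and Potential Benefits: "Minor toxicities will be treated by simply stopping the infusion and watching the patient for 6hr". The same section has such women unblinded through the pharmacy.
- Statistical Analysis: pain scores go to a two-way repeated-measures ANOVA, or to the Friedman test if not normal.

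The document does not define treated or early termination, and it gives no replacement rule, analysis population or missing-data method. It does not say whether scoring continues once an infusion has been stopped.

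**The concern.** Screen failures and early terminations are different events. A screen failure comes before randomization and can be made up freely. An early termination may come after the randomized solution has been given, and the reason may then depend on the arm: uncontrolled pain is more plausible on saline, and local anesthetic toxicity on ropivacaine. Pooling the two as grounds for over-enrolment lets a site treat both alike.

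There is a second route to the same result. In their usual forms, repeated-measures ANOVA and the Friedman test need a complete set of scores. A woman whose scores end with her infusion could leave the primary analysis even if nobody replaces her.

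Both routes select on outcomes that the trial measures. Movement pain is the primary outcome, and local anesthetic side effects are a listed secondary outcome. Losing the saline women with the most pain makes saline look better and hides benefit. Losing ropivacaine women with toxicity understates harm: with 20 per arm, each such woman is 1/20 = 5 percentage points of her arm's rate. Because toxicity leads to unblinding, the decision whether she counts could be made with her arm known.

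**Working it through.** **The plan's own figures.** The overage is 70 − 60 = 10, which is 10/70 = 14.3% of those enrolled, and 60/(1 − 1/7) = 70, so the figures are coherent. Ten is a ceiling on all losses, including screen failures.

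Statistical Analysis gives beta "risk of 0.2, and an effect size involving a 40% reduction in pain scores, we estimate that 20 patients are needed in each arm". No mean, SD or named test is stated, so 20 per arm cannot be reproduced. Solving backwards for a two-sided 0.05 test at 80% power (normal approximation), the standardized effect is (1.960 + 0.842) × √(2/20) = 0.886. A 40% reduction then implies SD/control mean = 0.40/0.886 = 0.451.

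**Shift in the saline mean.** Assumptions, none of them in the documents: normal scores, SD 20 mm, saline mean 50 mm. The assumed SD/mean ratio is 20/50 = 0.40, close to the implied 0.451, and the planned effect would be 0.40 × 50 = 20 mm. If the fraction p with the most pain is lost, the mean of those left falls by SD × φ(z)/(1 − p), where z is the upper-p normal quantile. If stopping correlates only r with pain, multiply by r. The mean shift is the same whether the women are dropped or replaced by women who do not stop; only the arm size differs.

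| p lost | φ(z)/(1 − p) | fall, r = 1 | share of 20 mm | fall, r = 0.5 |
|---|---|---|---|---|
| 5% | 0.109 | 2.2 mm | 11% | 1.1 mm |
| 10% | 0.195 | 3.9 mm | 20% | 1.95 mm |
| 15% | 0.274 | 5.5 mm | 27% | 2.7 mm |

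The falls scale in proportion to the SD. The r = 1 column is an upper bound for a given p.

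**Effect on the test.** This is a simulation of 20,000 runs, comparing two arms with 20 analysed in each by a two-sided t-test at 0.05. In the saline arm, the k women with the highest stopping score are excluded and replaced; the ropivacaine arm loses nobody. A single-score t-test stands in for the planned repeated-measures analysis.

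| k replaced | shift in SD (r = 1 / 0.5) | power at true effect 0.886 SD (r = 1 / 0.5) | rejection with no true effect (r = 1 / 0.5) |
|---|---|---|---|
| 0 | 0 | 0.78 | 0.05 |
| 1 | −0.10 / −0.05 | 0.71 / 0.74 | 0.07 / 0.05 |
| 3 | −0.23 / −0.12 | 0.59 / 0.68 | 0.14 / 0.07 |
| 5 | −0.34 / −0.17 | 0.47 / 0.62 | 0.23 / 0.09 |

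The extra rejections with no true effect come from saline looking better than it is, so they do not favour ropivacaine.

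**The case against.** A reader might infer that the plan replaces women who stop, that the arms will hold only completers, or that stopping the pump amounts to leaving the study. The documents do not support any of these.

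- The target is women randomized and treated, not completers. A woman who was bolused and later stopped meets it, and no section orders her replacement or exclusion. Replacing her would also mean randomizing more than the 60 in the preceding sentence.
- Early terminations have a harmless meaning. Assignment precedes the spinal and the bolus comes at the end of surgery, so a woman can be lost in between. Only the preparing pharmacist knows the solution, so such losses should not depend on arm.
- Participant Selection says that a woman may withdraw because the pump is easily stopped, not that stopping the pump withdraws her. The toxicity rule stops the infusion and observes her; it does not remove her from the study. Objectives lists ropivacaine side effects and their treatment as data to be collected, which would make little sense if those women were dropped.
- Pain-driven withdrawal may be rare. All arms have stepped rescue medication, and the usual care described under Patient Safety and Potential Benefits uses the same drugs.
- The illustration rests on assumed inputs and on loss from one arm. Similar loss from the ropivacaine arms would largely cancel in the pain difference.

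All of this stands, and it limits the point to what the wording permits. It does not close the gap. Two readers could assemble different sets of 60 from the same sentence. The harmless reading also does not settle follow-up after stopping, or what the planned tests do with incomplete records.

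**Conclusion.** The point holds as a permissive gap in the wording: arm-related replacement or loss after the bolus is possible but not prescribed. Its size is unknown, because the documents give no stopping rate, mean or SD. Under the stated assumptions, losing 5–15% of saline women lowers the saline mean by about 2 to 5.5 mm if those lost are exactly the women with the most pain, and by about 1 to 3 mm at correlation 0.5. The direction on pain is toward hiding benefit; on toxicity it is toward understating harm. The ten extra enrolments should not be read as a forecast of ten replaced women. This is a cheap improvement to the text. It implies no change to the sample size.

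**What to change.** - **Abstract, enrolment sentence:** allow replacement only for women who never receive the study bolus. Count every bolused woman toward the 60 and analyse her in her randomized arm.
- **Participant Selection:** state that stopping the infusion, for any reason, is not withdrawal from the study. Scheduled pain scores, rescue records and telephone calls continue unless the woman declines.
- **Reporting:** give terminations by arm and reason, separating those before the bolus from those after it.

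Some women will still lack later scores, so Statistical Analysis should name a method that keeps partial records (a mixed model, for example), with a sensitivity analysis for the missing scores.

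The cost is a few sentences, with no additional patients or visits. The downside is that some of the 60 will have had a shortened infusion, so the estimated effect may be slightly smaller.

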### **Introduction and Background:**

The primary hypothesis of this study is that post-cesarean section pain with movement will be significantly improved in women treated with IT PFM by the addition of continuous subfascial wound infiltration with ropivacaine. There are approximately 4 million deliveries in the United States every year; with about 30% of these deliveries being cesarean sections. This makes cesarean section one of the most common surgeries performed today. Women experience significant post-operative pain after cesarean sections. Cesarean section patients are unique among surgical patients in that they have to immediately care for their newborns after their procedure, and their infants may be affected by systemically-administered maternal pain medications if breastfeeding. Therefore, this population requires the combination of maximal pain relief with minimal sedation, while minimizing the exposure of infants to clinically-significant amounts of drugs in breast milk. This encourages further studies that will elucidate better means of accomplishing ideal post-operative pain.

Pain, both intraoperative and postoperative, has been shown to be the anesthetic outcome of greatest concern to women undergoing cesarean section with the potential side effects of pain relief being of much less concern (1). This was found to be true both in terms of absolute ranking and when using a relative value score. Pain as part of the childbirth experience may predispose the parturient to the development of post-traumatic stress disorder (2). It has also been suggested that pain after cesarean section decreases the effectiveness of breast feeding leading to more formula and pacifier use (3, 4). In addition to the obvious psychological aversion to pain by patients, it is well-known that pain can stimulate a variety of potentially detrimental physiological effects such as tachycardia, hypertension, respiratory splinting, and inactivity, which in turn can lead to

IRB00073292

risks of myocardial infarction, aneurysmal rupture, thrombophlebitis, post-operative atelectasis and pneumonia. Poorly controlled post-surgical pain relief also influences the risk of developing chronic post-surgical pain (CPSP) (5, 6). CPSP is defined as pain of at least 2mo duration which develops after a surgical procedure, and which is not related to any other causes of pain (infection, malignancy, etc.) or to pain continuing from a pre-existing pain problem (7). The incidence of CPSP after cesarean section is believed to be between 10-12% (5, 6), meaning that as many as 168,000 women might be affected with this each year. Even more troubling is that an estimated 4% of the women undergoing cesarean section (~48,000) actually develop disabling chronic pain defined as pain > 5 on a scale from 0 to 10 (6). Recognition of the above psychological and physical attributes of pain led to the Joint Commission recommendation to treat pain as the fifth vial sign, with the stated goal for US healthcare facilities to uniformly achieve pain scores  $\leq$  3 out of 10 (8).

Pain after cesarean section has two well-recognized components – somatic and visceral. Somatic pain is often described as a well-localized, sharp, burning, or tearing pain. In contrast visceral pain is described as a poorly-localized, dull or cramping pain. Somatic pain has both cutaneous and deep components which are transmitted via the anterior components of the spinal nerves, whereas visceral pain is a sympathetically-mediated pain whose sensation returns via afferents from the uterus to the inferior hypogastric plexus, and hence into the sympathetic chain, ultimately arriving at the spinal cord (8). It is a well-accepted theory that multimodal pain relief helps to alleviate pain by both working on different types of pain (somatic vs visceral) and at different pain receptors leading to either additive or synergistic analgesia, while minimizing the side-effect profile of any single drug component of the analgesic cocktail (9). For instance, either systemic or neuraxial opioids are traditionally given after cesarean section to decrease post-operative pain. Unfortunately, opioids given by either of these routes have several undesired and potentially severe side-effects including pruritus, constipation, urinary retention, nausea/vomiting, sedation, and respiratory depression (10). In an effort to mitigate these troublesome issues, NSAIDs are commonly given to reduce the inflammation associated with surgical injury, thereby decreasing the inflammatory

component of the pain with a resulting opioid-sparing effect (8, 10). Additionally, NSAIDs are particularly effective against the visceral cramping pain which results from uterine involution (8).

While the combination of neuraxial opioids with systemic NSAIDs appears to provide excellent postoperative pain relief at rest during the first 24hr, a significant number of women experience pain greater than 3/10 with movement during this same period, and with both rest and movement pain at time periods greater than 24hr. These pain exacerbations primarily involve discomfort resulting from tension on the wound, often require treatment with IV or PO opioids, and appear to be due largely to cutaneous or deep somatic pain. As incisional pain can often be acutely managed with local anesthetic (LA) infiltration, interest grew in seeing if continuous local infiltration of LA alone, NSAIDs alone, or combinations of NSAIDs with LAs through a catheter inserted into the surgical wound could reduce both post-surgical pain and postoperative opioid consumption. Initial results using subcutaneous catheters were disappointing, showing at most modest reductions in opioid use, with little or no change in pain scores (11). For example, in one study comparing the subcutaneous infusion of 4ml/hr of 0.25% bupivacaine with a saline infusion control showed no difference in VAS for pain at rest, but showed a 22 mg reduction in morphine use over 24hr (12). However, a meta-analysis of a number of trials involving subsets of surgical patients showed both reductions in pain scores and opioid consumption in the obstetric/gynecologic surgery population, although only pain at rest was examined (11). Multiple studies involving cesarean section patients have shown that subfascial infusions of plain 0.2% ropivacaine (13), 0.25% levobupivacaine (14), 0.2% ropivacaine containing diclofenac (15), or 0.2% ropivacaine with ketoprofene (16) all provide good postoperative analgesia and a reduction in opioid usage for post-operative pain. In one of these studies (16), wound infusion of identical solutions through either subfascial catheters or subcutaneous catheters was compared, and subfascial administration was shown to be clearly superior based on pain at rest and total postoperative morphine consumption. Additionally, in two of the above studies, continuous wound infusion was found to provide postoperative analysis nearly equivalent (14) or better (13) than epidural analgesia with either LA or PFM,

respectively. In contrast to these positive studies, one negative study found that subfascial wound infusion with 5ml/hr of 0.375% ropivacaine was inferior to intrathecal PFM in terms of both pain scores and IV oxycodone use (17). Therefore, while there are both theoretical and evidential grounds to support the use of subfascial wound catheters, their absolute efficacy as sole agents for pain relief remains to be established.

To date, long-acting neuraxial opioids like PFM provide the gold standard for postcesarean delivery analgesia whether given via the IT or epidural route, providing excellent pain relief for the first 24hr while allowing the mother to ambulate and care for her child (18, 19). However, it is clear that neuraxial opioids do not provide complete analgesia for cesarean section when used as primary agents, with more than 70% of patients requesting further analgesia (19). Even when codeine with acetaminophen is given prn, 33% of women in one study still experienced inadequate analgesia (18). Pain with movement appears to be the most poorly treated pain phenomenon using neuraxial PFM (19). Again, this points to the importance of multimodal pain control in obstetric patients. Surprisingly, while continuous wound infiltration has been examined as a primary technique for post-cesarean pain relief (13,14,15,16) and has even been compared for efficacy to epidural (13,14) and IT (17) post-cesarean analgesia, no one has tested to see if continuous wound infiltration with LAs improves the analgesia obtained from IT PFM. However, it is standard practice of some obstetricians in our institution to use the continuous wound infiltration system on every patient undergoing a cesarean section whether they have IT PFM or not. The purpose of the proposed study is to examine the hypothesis that continuous wound infusion with ropivacaine using a highvolume, low-dose protocol will significantly improve pain with movement after cesarean section in patients who have received our standard dose of IT PFM. A control group (IT PFM + saline wound infusion) will be compared to two groups receiving both IT PFM along with one of two doses of ropivacaine (experimental groups) using the OnQ® elastomeric pump for delivery of the infusions. We have purposefully used lower concentrations of ropivacaine (0.1-0.2%) along with higher volumes in recognition that the nerves to be anesthetized are of smaller diameter, and therefore require lower concentrations of LA for this effect; while ensuring a high enough volume to completely

bathe the wound at the subfascial layer. During both cesarean section under local anesthesia (20), and with transversus abdominis plane blocks for post-operative analgesia (21) - situations which involve some of the same sensory nerves blocked by continuous wound infusion - the importance of volume versus concentration of LAs has been stressed. It is expected that ropivacaine, used in conjunction with IT PFM, will provide additive or synergistic pain relief as compared to IT PFM alone, and hopefully this will lead to better breast feeding, decreased opioid use with less opioid side-effects, fewer prolonged stays secondary to pain issues, increased patient satisfaction, and ultimately to decreased hospital costs.

